**a) Reduce the number and severity of hypoglycemic events**

*Hypothesis: Use of CGMs will provide real-time blood glucose trends, allowing hypoglycemia to be predicted and prevented, or detected and treated before becoming severe or symptomatic.*

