Infants will be randomized to a "CGM Protocol" or a "Standard of Care" group. We aim to enroll ten patients in each study arm. Those on the CGM Protocol will have a fully accessible CGM that will be analyzed in real-time for blood glucose trends and will alarm for any blood glucose level approaching hypoglycemic threshold. The CGM alarm will sound if blood glucose is less than 60 mg/dL for all patients. The CGM will also alarm if the rate of drop in blood glucose is greater than 20 mg/dL/minute and thus concerning for impending hypoglycemia. These thresholds are programmed into the CGM by a study team member and will not be modifiable by the medical team. Those in the "Standard of Care" group will have a CGM in place but live readings will not be available to the clinical team. However, the research team will review CGM data from the "Standard of Care" group daily and if a subject in the "Standard of Care" group has three episodes of unrecognized severe hypoglycemia (eg. BG <40 mg/dL), the study team will alert the NICU providers. Notification will occur immediately following identification of the third unrecognized severe episode of hypoglycemia, which will at most be 24 hours after the event occurred.

For subjects in the "CGM Protocol" group, whenever the CGM alarms or there is a concerning blood glucose trend according to the CGM, the nurse will be asked to check a blood glucose value. All clinical

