management decisions will be made by the clinical team based on laboratory or bedside monitor-confirmed blood glucose values. The CGMs will be calibrated, at a minimum, every 12 hours with a blood glucose value measured by bedside glucometer. Additional calibrations will be performed if more frequent blood glucose monitoring is deemed necessary by the NICU team. In the “Standard of Care” group, the only change to current management is the potential performance of additional blood glucose checks that may be prompted if repeated unrecognized severe hypoglycemia is detected by the research team. The CGM will remain in place until the infant is no longer being monitored for glycemic stability or until the infant is discharged. If hypoglycemia work-up and management lasts longer than a week, the CGM sensor will be replaced on the seventh day after initial insertion. In the case of a sensor dislodgement or malfunction, it would also be replaced. Lastly, if a patient continues to have unstable hypoglycemia for longer than 28 days (eg. four 7-day cycles of CGM) then their study participation will also end at that time.

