### *e. Study Timeline*

Subjects will be enrolled ideally within 24 hours of diagnosis of hypoglycemia. The CGM will remain in place until the subject is on a sustainable feeding regimen and no longer having hypoglycemia. The CGM will be removed 24-48 hours after the NICU team has deemed the hypoglycemia resolved or stable enough for its continued management at home. We expect most patients to be in the study for at least a week but duration can vary significantly depending on the etiology of the hypoglycemia and how challenging it is to control. In the event that a patient continues to have unstable hypoglycemia 28 days after randomization into the study, then study participation will conclude on the 28th day and the CGM will be removed at that time. We expect to carry on the study for approximately 18 months.

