## 8. Data Analysis Plan

Hypoglycemia will be defined as a laboratory or bedside monitor blood glucose value of <50 mg/dL prior to 48 hours of life and <70 mg/dL after 48 hours of life or CGM values below threshold for >30 minutes with no concomitant blood sugar reading. Hypoglycemic episodes within one hour of each other will be considered as one event. Severe hypoglycemia will be defined as less than 40mg/dL. Euglycemia will be defined as 48 hours with blood glucose equal or greater than 70mg/dL after 48 hours of life or equal or greater than 50mg/dL if before 48 hours of life.

We will record all blood glucose levels, laboratory data related to the investigation of the underlying cause of hypoglycemia, intravenous and enteral sources of glucose, and other related therapeutic interventions such as administration of diazoxide, octreotide, glucocorticoids, and carnitine. Data analysis will begin by comparing blood glucose data with information from the CGM monitors to assess for accuracy of the CGMs. This will be done by calculating the mean-absolute-relative-difference (MARD) between sensor-measured glucose levels and laboratory or bedside meter-measured blood glucose values. We will then compare the severity and frequency of hypoglycemia, as well as the time to diagnosis and time to euglycemia on a sustainable feeding regimen between the “CGM Protocol” and “Standard of Care” groups. Chi-squared analysis will be used to assess differences in the incidence of hypoglycemia while the Mann-Whitney U test will be used to analyze differences in time-to-diagnosis and time-to-euglycemia.

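### Section 8 tests the number and severity of recurrent events only by chi-squared on incidence: no per-infant measure, time denominator or severity test is given

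*Combined protocol and SAP*

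**What the plan says.** Aim (a) in Section 1 is: "Reduce the number and severity of hypoglycemic events". Section 4c calls the primary endpoint incidence and severity; Section 9 calls it frequency and severity. Section 8 opens the comparison broadly: "We will then compare the severity and frequency of hypoglycemia". It then names one test for any of this: "Chi-squared analysis will be used to assess differences in the incidence of hypoglycemia". The Mann-Whitney U test is reserved for time-to-diagnosis and time-to-euglycemia.

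Section 8 does define an event. A single low blood value counts, "or CGM values below threshold for >30 minutes with no concomitant blood sugar reading" also counts, and episodes within an hour are merged. Severe means below 40 mg/dL.

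Monitoring time follows the infant's course. Section 4a says: "The CGM will remain in place until the infant is no longer being monitored for glycemic stability or until the infant is discharged". Section 4e ties removal to hypoglycemia being judged "resolved or stable enough for its continued management at home", caps participation at 28 days, and adds: "We expect most patients to be in the study for at least a week but duration can vary significantly".

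Section 9 sets 10 infants per arm without a power calculation, on the ground that this lets the variance of the primary outcome be assessed for a larger study.

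**The concern.** An outcome made of repeated events needs three things before it can be compared: a value for each infant, a time base for that value, and a test that respects the infant as the randomized unit. Section 8 supplies an event definition and a test for proportions, and nothing between them.

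- **Number of events.** Counting infants with any event treats one episode and fifteen as the same result, although the aim is to reduce the number.
- **Time.** Infants are watched for different lengths of time. The third hypothesis in Section 1 is that CGM shortens time to stable glucose, and stability is what ends monitoring. Time at risk may therefore differ by arm.
- **Severity.** It is half of the primary outcome. It has a threshold but no measure and no test.
- **Purpose.** The pilot is meant to inform the sample size of a larger trial. A variance can be estimated only for a defined quantity. Choosing that quantity after seeing 20 infants would make the planning figure data-driven.

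**Working it through.** The plan states no alpha, rate, effect or SD, so it has no figure to reproduce. I read the test sentence in both ways open to it and worked out what each does.

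**Inputs.** From the documents: 10 infants per arm; two episodes required at entry; most infants expected to stay at least a week. Assumed: two-sided 0.05; 0.25 to 2 events per day in Standard of Care; 7 days observed, so the mean count m is 1.75 to 14; infant rates gamma-distributed with shape k from 0.5 (large differences between infants) to 4 (small); a true effect that halves the rate.

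**Reading 1: infants with any event, yes or no.** P(any event) = 1 − [k/(k+m)]^k.
- Lowest rate, k = 0.5: 1 − (0.5/2.25)^0.5 = 53%. After halving (m = 0.875): 1 − (0.5/1.375)^0.5 = 40%.
- Highest rate, k = 4: 1 − (4/18)^4 = 99.8%. After halving (m = 7): 1 − (4/11)^4 = 98.3%.

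In the second case the event count halves and the tested proportion moves by 1.5 points. If all 10 Standard of Care infants have an event, 7 of 10 in the CGM arm gives chi-squared = 20 × (10×3 − 0×7)² / (10×10×17×3) = 3.53, p = 0.060. It takes 6 of 10 or fewer: 20 × (10×4)² / (10×10×16×4) = 5.0, p = 0.025.

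**A per-infant count for comparison.** Yes/no power is by exact enumeration of the 2×2 tables (uncorrected Pearson). The Mann-Whitney and pooled columns are from 20,000 simulated trials per scenario; the corners of the 16 scenarios and one middle case are shown.

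| Events/day | k | Yes/no power | Mann-Whitney power | Mann-Whitney type I | Pooled-event type I |
|---|---|---|---|---|---|
| 0.25 | 0.5 | 8% | 10% | 4% | 34% |
| 0.25 | 4 | 15% | 25% | 4% | 10% |
| 1 | 1 | 5% | 19% | 4% | 48% |
| 2 | 0.5 | 5% | 11% | 5% | 72% |
| 2 | 4 | 0% | 62% | 5% | 36% |

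The count does better in all 16 scenarios, but by only 2 points in the first row.

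**Reading 2: events pooled by arm.** The variance of a total is inflated by 1 + m/k. At 1 event per day and k = 1 this is 1 + 7/1 = 8, so the type I error is about P(|Z| > 1.96/√8) = 49%, against 48% simulated. Across the scenarios it runs from about 10% to 72%.

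**Monitoring time.** With one event per day in both arms, 10 days against 7 days gives 10 against 7 events, an apparent 30% reduction with no change in rate. In 4,000 simulated trials at one event per day with no differences between infants, letting monitoring vary (log-normal, median 7 days, limited to 2-28) raised the type I error of pooled totals from 4.6% to 39.8%. A Mann-Whitney test on events per monitored day stayed at 4.0-4.9% in all six settings tried.

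**Precision of the SD.** With 10 infants, a normal-theory 95% interval for the SD runs from √(9/19.02) = 0.69 to √(9/2.70) = 1.83 times the estimate. For skewed counts it is worse: the sample SD ranged from 0.24 to 2.05 times the true SD at the worst shape.

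**The case against.** **The natural reading works.** Infants are randomized, Section 4c speaks of incidence in infants, and chi-squared suits a yes/no outcome. A reader might infer that the primary comparison cannot be carried out at all. The documents do not support that: the event and merging rules are stated, so the yes/no analysis can be run. What stands is that it answers a narrower question than the aim.

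**Nobody says events will be pooled.** A reader might also infer that the plan carries a false-positive rate of up to 72%. No section states that reading. The figure shows only why the unit should be written down.

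**Frequency could mean a rate.** Then monitored time would be covered. But the word appears without a denominator, and the named test is not one for rates.

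**Saturation is assumed.** Two episodes before entry do not fix the rate afterwards. At the low end only 53% of infants have an event and the gain from a count is small. This stands.

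**It is an unpowered pilot, and counts can be derived later from stored data.** Both are true, so nothing is irretrievably lost. Even so, the variance promised in Section 9 needs a quantity chosen before the data are seen.

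**A per-infant count does not remove unequal detection.** Section 4a sets a prompt for extra blood sampling in the CGM Protocol arm: "whenever the CGM alarms or there is a concerning blood glucose trend according to the CGM, the nurse will be asked to check". Standard of Care infants get prompted checks only after three unrecognized severe episodes. A prompted check may catch a brief dip that would otherwise not count, or may replace a sustained CGM low with a normal blood value. It is tempting to infer a bias in a known direction; the documents do not show one. If detection alone multiplied CGM-arm counts by 0.67 or 1.5, the per-infant test would reject in 6-29% of trials with no true effect. That calls for a sensitivity analysis and is not a reason to keep the yes/no test.

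**Conclusion.** The point holds as a specification that should be repaired before analysis. For a primary outcome of number and severity of recurrent events, Section 8 names a test that ignores number, gives no time base, and leaves severity without a measure or test. Under the assumed rates, yes/no power for a halving is 0-15%, against about 10-62% for one count per infant, whose type I error is 4-5%. These figures depend on assumed rates, a 7-day window and equal detection in both arms, and they illustrate information lost; a declared pilot is not at fault for low power. The consequence that needs no assumption is that Section 9's variance refers to a quantity the plan never defines.

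**What to change.** In Section 8, replace the chi-squared sentence with the following.

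1. **One value per infant.** Either events per monitored day, or the event count in a fixed window from randomization (for example 7 days), with the other as a sensitivity analysis. If the window is chosen, say how days after CGM removal are counted.
2. **Test.** Exact Mann-Whitney or permutation test between arms.
3. **Severity.** Events below 40 mg/dL per infant, analysed in the same way, stating whether CGM values count toward them.
4. **Planning figures.** Infant-level mean and SD by arm, described as imprecise with 10 infants.
5. **Detection.** A sensitivity analysis that applies one event definition to the CGM trace identically in both arms, for example below threshold for more than 30 minutes regardless of blood readings.

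All infants wear a CGM and all blood values are recorded, so no new data or patients are needed. There are costs. A fixed window leaves out later events. A rate is unstable for short stays, and its denominator may be affected by the intervention. Counts from the CGM trace carry sensor error.

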**c) Reduce the time taken to achieve stable euglycemia on a sustainable feeding regimen.**

*Hypothesis: CGMs will shorten time to achieving a stable, normal blood glucose concentration on a sustainable feeding regimen.*

By performing a pilot study we hope to test the feasibility of our study design. We plan to use the results to assess the validity of our chosen outcome measures, inform power and sample size considerations and test the practicality of our study timeline for larger-scale study on the same topic. The results of this study could potentially alter the way neonatal hypoglycemia is routinely managed and thereby improve neurodevelopmental outcomes in this population.

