## 7. Quality Control Method

We will use checklists to verify that every subject has undergone appropriate consent, eligibility screening and safety monitoring during the study. Appropriate CGM placement and function will be performed daily on all enrolled subjects. Glucose data from CGM monitors will be compared to sampled blood glucose levels to assess for accuracy of the CGMs. We will also maintain a log of any protocol deviations and reportable events.

Criteria for early termination of study participation:

- Development of widespread skin disease such that placement of a CGM sensor would be difficult to secure
- Development of infection or colonization with multi-drug resistant organisms (i.e. MRSA, VRE, ESBL producing bacteria)
- Development of significant erythema, induration, infection or other adverse event at the CGM insertion site
- Study cancellation by the sponsor.
- Participant/family failure to follow the study requirements.
- The Principal Investigator judges it is in the best interest for the child to be taken off the study.
- Parent withdraws permission for the child to participate in the study.

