## 9. Statistical Power and Sample Considerations

This is a feasibility study and therefore is not powered; however, the choice of 10 subjects in each of two groups is generally considered acceptable for feasibility/pilot studies and should allow the variance in the primary outcome (decrease in frequency and severity of hypoglycemia with use of CGMs) to be formally assessed for use in a subsequent larger study.

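### The Mann-Whitney test in Section 8 has no rule for infants who leave without the event at different times; the secondary time outcomes should get a modest censoring-aware analysis

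*Combined protocol and SAP*

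**What the plan says.** Section 4c names three secondary time outcomes: to diagnosis, to treatment initiation, and to euglycemia on a sustainable feeding regimen. For the first and third, Section 8 states that "the Mann-Whitney U test will be used to analyze differences in time-to-diagnosis and time-to-euglycemia". It assigns no analysis to the second. No start point is stated for any of them, and there is no censoring, ranking or missing-data rule.

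The event and the exits are described as follows.

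- **Event.** In Section 8, "Euglycemia will be defined as 48 hours with blood glucose equal or greater than 70mg/dL" once the infant is past 48 hours of life, with a lower threshold before that.
- **Discharge or home management.** Section 4a keeps the sensor in place "until the infant is no longer being monitored for glycemic stability or until the infant is discharged". Section 4e has it "removed 24-48 hours after the NICU team has deemed the hypoglycemia resolved or stable enough for its continued management at home".
- **Day 28.** Section 4e ends participation on the 28th day: "In the event that a patient continues to have unstable hypoglycemia 28 days after randomization into the study".
- **Early termination.** Under "Criteria for early termination of study participation", Section 7 lists seven reasons, among them insertion-site reactions, investigator judgement and parental withdrawal.

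On purpose, Section 1 says the results will be used to "assess the validity of our chosen outcome measures, inform power and sample size considerations". Section 9 says the study is not powered and that ten infants per arm "should allow the variance in the primary outcome" to be assessed.

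**The concern.** A Mann-Whitney test compares complete values or ranks. An infant who leaves on day 5 without the event is known only to have an event time beyond day 5. That infant cannot be ranked against one who reached the event on day 9. The analyst must drop the infant, treat day 5 as the event, or assign a worst rank, and the plan does not say which.

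These choices give different answers, and with 20 infants one or two of them can matter. If the choice is made after the data are seen, it can shape the secondary estimates. Those estimates are part of what the pilot passes to the larger study, including whether the time outcomes can be measured at all. No confirmatory conclusion is at stake.

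**Working it through.** The plan gives no event time, exit rate or effect size, so there is no figure to reproduce. From the documents come 10 infants per arm, the 28-day limit and the exit routes. Exponential event times, the medians and the exit rates are assumptions. P is the probability that a CGM Protocol infant reaches the event before a Standard of Care infant.

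**1. Day-28 limit only.** With median m, the share without the event at day 28 is S = 2^(-28/m). Subscript 1 is CGM Protocol, 2 is Standard of Care, and m2 = 2 × m1, so the true P is 2/3 = 0.667.

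- Infants without the event: 10 × (S1 + S2).
- P with these infants dropped: [(1 − S2) − (1 − S1·S2)/3] / [(1 − S1)(1 − S2)].
- P with these infants tied last: 2/3 − S1·S2/6.

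At 7 v 14 days, S1 = 0.0625, S2 = 0.25 and S1·S2 = 0.0156. Without the event: 10 × 0.3125 = 3.1 infants. Dropped: (0.75 − 0.328)/(0.9375 × 0.75) = 0.600. Tied last: 0.667 − 0.003 = 0.664.

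| Medians (days) | Without event, of 20 | P, dropped | P, tied last |
|---|---|---|---|
| 3 v 6 | 0.4 | 0.654 | 0.667 |
| 5 v 10 | 1.6 | 0.625 | 0.666 |
| 7 v 14 | 3.1 | 0.600 | 0.664 |

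Medians among infants with the event at 7 v 14 are 6.4 v 9.5, a difference of 3.1 days instead of 7.0. So the day-28 limit alone does no material harm if those infants share the worst rank.

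**2. Early exits, equal in both arms.** Suppose 10%, 20% or 30% of infants have an exit time uniform on days 1-14. At 7 v 14, 1.2, 2.4 or 3.6 of 20 leave before the event. Exit time used as event time gives P = 0.653, 0.642 or 0.631. At 3 v 6 with 20%, P is 0.657.

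The true 28-day restricted mean is (m/ln 2)(1 − S): 10.10 × 0.9375 = 9.5 and 20.20 × 0.75 = 15.1 days, a difference of 5.7. At 20%, exit as event gives 8.6 v 13.3, a difference of 4.8 before rounding. Kaplan-Meier with censoring at exit recovers 9.5 v 15.1.

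**3. Discharge shortly before the event is documented.** Suppose 20% are discharged 0-2 days before it, at 7 v 14.

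| Rule | Restricted means (days) | Difference |
|---|---|---|
| Truth | 9.5 v 15.1 | 5.7 |
| Discharge counted as event | 9.3 v 15.0 | 5.7 |
| Censored at discharge | 11.1 v 16.8 | 5.7 |

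The arm difference survives either rule. Censoring makes each arm's mean about 1.6-1.7 days too long, because this kind of discharge is informative.

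**4. Unequal exits.** Rejection rates at nominal two-sided 0.05 from 4,000 simulated pilots per row, with Standard of Care median 7 days, a 28-day limit and exit independent of the event (Monte Carlo standard error at most about 0.008):

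| Hazard ratio | Exit, Standard of Care v CGM Protocol | Exit as event | Worst rank | Events only | Log-rank |
|---|---|---|---|---|---|
| 1 | day-28 limit only | 0.047 | 0.047 | 0.043 | 0.061 |
| 1 | 20% v 20% | 0.057 | 0.051 | 0.051 | 0.068 |
| 1 | 0% v 40% | 0.171 | 0.135 | 0.091 | 0.062 |
| 2 | 20% v 20% | 0.250 | 0.128 | 0.169 | 0.260 |
| 2 | 0% v 30% | 0.475 | 0.061 | 0.290 | 0.246 |
| 2 | 30% v 0% | 0.108 | 0.377 | 0.077 | 0.275 |

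With balanced exit, every Mann-Whitney coding holds its level. With unequal exit, the coding decides the result. The asymptotic log-rank test is slightly liberal at this size (0.053 to 0.068 over all patterns tried), which is why a permutation version is preferable.

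**5. Against pilot noise.** At 10 per arm the standard deviation of the estimated P is about 0.12. The largest shift in P in steps 1 and 2 is 0.667 − 0.600 = 0.067.

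**The case against.** The strongest reply is that few infants will be affected. Section 4e keeps the sensor until feeding is sustainable and hypoglycemia has stopped, which is close to the time-to-euglycemia event. Planned exit will therefore usually follow the event. This stands. Release as stable enough for home and early termination look like exceptions, although Section 4b excludes only expected stays under 24 hours, so a stay too short to document 48 hours is possible.

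A reader might infer that the 48-hour definition in Section 8 contradicts the 24-48 hour removal timing in Section 4e. It does not. One is an outcome definition and the other governs a device. The 48 hours may begin before the clinical judgement that triggers removal, and nothing says that blood glucose or chart data stop when the sensor comes off.

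A reader might also infer that Section 8 drops infants without the event. It does not say so; it is silent.

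The day-28 rule concerns continuing unstable hypoglycemia, so it bears on euglycemia. It does not show that diagnosis or treatment start goes unobserved, since Section 4d collects both every 2-3 days. This also stands, and the three outcomes need separate treatment. For diagnosis, the gap is that no section guarantees an etiology for every infant.

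Finally, the outcomes are secondary, the study is unpowered, and Section 9 mentions only the primary outcome's variance. That limits the reach and argues for a short fix. It does not remove the point: Section 1 makes testing the outcome measures a purpose of the pilot, and Section 4c says the larger study's comparisons will be powered from these data.

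**Conclusion.** The point holds with limited reach and should be corrected. The stated test cannot rank infants who leave at different times without the event, and no rule fills the gap. Under equal exit, the two naive codings pull the arm difference toward zero: P falls from 0.667 to 0.600 if day-28 infants are dropped, and to 0.642 if early exit times serve as event times with 20% exits (both at 7 v 14). Unequal exit could distort the result in either direction. It is plausible because only one arm's live readings reach clinicians, but no section gives a rate.

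The stronger reading, that the secondary results would be unusable or their type I error seriously inflated, is not supported. With balanced exit, Mann-Whitney error stays at 0.043 to 0.057. Inflation to 0.171 needs 0% v 40% exit, which is purely an assumption. All sizes here rest on assumed exponential times and assumed exit rates, and time-to-diagnosis and time-to-treatment were not modelled separately.

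**What to change.** Amend Section 8 as follows.

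- **Start point.** Measure all three times from randomisation, from which Section 4e already counts the 28 days.
- **Time-to-euglycemia.** Show Kaplan-Meier curves by arm and compare them with a permutation log-rank test, censoring at day 28 and at withdrawal or early termination. The permutation test is exact only if exit patterns are alike in both arms. Mann-Whitney with a shared worst rank is acceptable if day 28 turns out to be the only reason for having no event.
- **Discharge before documented 48-hour euglycemia.** Analyse it as the event at discharge and as censored at discharge, and report both.
- **Time-to-diagnosis.** Show cumulative incidence by arm among infants not yet diagnosed at randomisation, with resolution without an established etiology as a competing outcome.
- **Time-to-treatment initiation.** Summarise descriptively among infants not yet treated at randomisation.
- **All three.** Report the number without each event by arm and reason.

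The cost is wording in Section 8, slightly more analysis, and explicit recording of event, discharge and exit dates, many of which may already be retrievable from the case histories in Section 6. The fix does not buy precision: at 7 v 14 days with 20 infants, the interval for the 28-day restricted mean difference is about plus or minus 8.5 days.
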